4.5.7 Disease-related symptoms

Disease-related symptoms (cough, hemoptysis, pain, dyspnea, fatigue, cachexia, vision impairment, vertigo) will be collected at each tumor assessment to evaluate the relationship between those symptoms and disease progression.

4.5.8 Laboratory, Biomarker, and Other Biological Samples

Samples for the following laboratory tests will be sent to the study site's local laboratory for analysis:

- Hematology: WBC count, RBC count, hemoglobin, hematocrit, platelet count, and differential count (neutrophils, eosinophils, basophils, monocytes, and lymphocytes)
- Chemistry panel (serum or plasma): bicarbonate or total carbon dioxide (if considered standard of care for the region), sodium, potassium, magnesium, chloride, glucose, BUN or urea, creatinine, total protein, albumin, phosphate, calcium, total bilirubin, ALP, ALT, AST, and LDH
- Coagulation test: INR and aPTT
- Thyroid-function testing: thyroid-stimulating hormone, free triiodothyronine (T3) (or total T3 at sites free T3 is not performed), and free thyroxine (also known as T4)

- [REDACTED]
 - [REDACTED]
 - [REDACTED]
 - [REDACTED]

[REDACTED]

- [REDACTED]
- [REDACTED]
 - [REDACTED]
 - [REDACTED]
- [REDACTED]
 - [REDACTED]
- Pregnancy test

All women of childbearing potential (including those who have had a tubal ligation) will have a serum pregnancy test at screening. During the study, urine pregnancy tests will be performed on Day 1 of every cycle and after study treatment is discontinued (see [Appendix 1](#)). If a urine pregnancy test is positive, it must be confirmed by a serum pregnancy test.

A woman is considered to be of childbearing potential if she is postmenarcheal, has not reached a postmenopausal state (≥ 12 continuous months of amenorrhea with no identified cause other than menopause), and is not permanently infertile due to surgery (i.e., removal of ovaries, fallopian tubes, and/or uterus) or another cause as determined by the investigator (e.g., Müllerian agenesis).
- Urinalysis: pH, specific gravity, glucose, protein, ketones, and blood; dipstick permitted

Samples for the following analyses will be sent to one or several central laboratories or to the Sponsor or a designee for analysis. Instruction manual and supply kits will be provided for these central assessments. Refer to the laboratory manual for additional details on sample handling.

Assessments Performed on Blood Samples

The following assessments will be performed on the blood samples:

- PK assays

Serum samples will be obtained from patients in the experimental arm for measurement of tiragolumab and atezolizumab concentrations using validated assays.
- ADA assays

Serum samples will be obtained from patients in the experimental arm for measurement of ADAs to tiragolumab and to atezolizumab using validated assays.
- [REDACTED]

[REDACTED]

[REDACTED]
- Auto-antibody assays

Serum samples collected for the assessment of PK, ADAs, or biomarkers at baseline on Day 1 of Cycle 1 prior to the first dose of study treatment, may be used for auto-antibody testing if an immune-mediated adverse event develops in a patient that would warrant such an assessment.
- WGS

A single blood sample will be collected for WGS and may be sent to one or more laboratories for analysis. WGS data and associated clinical data may be shared with researchers who are not participating in the study or may be submitted to government or other health research databases for broad sharing with other researchers to perform research on human health and disease. Study participants will not be identified by name or any other personally identifying information.

WGS is contingent upon the review and approval by each site's IRB/EC and, if applicable, an appropriate regulatory body. If the site has not been granted approval for WGS, this assessment will not be applicable at that site.

WGS data will be analyzed in the context of this study and explored in aggregate with other studies to better understand disease pathobiology and adverse events and guide the development of new therapeutic approaches. Given the complexity and exploratory nature of these analyses, WGS data and analyses are for research purposes only and will not be shared with investigators or study participants.

Assessments Performed on Tumor Samples

The following assessments will be performed on tumor samples:

- [REDACTED]
- [REDACTED]

Patients having additional tissue samples from procedures performed at different times during this study will be requested (but not required) to also submit these samples for central testing. Tissue samples will be obtained at multiple times for individual patients will greatly contribute to understanding an improved understanding of the mechanism of action of the treatment and disease biology.

- For patients with non-squamous NSCLC, if *EGFR* and/or *ALK* status is unknown, these must be assessed locally or at a central laboratory (see Section 4.1.2 for exclusion criteria). [REDACTED]

[REDACTED]

- Biomarker assays in mandatory biopsy at disease progression

Patients in both treatment arms will undergo a mandatory tumor biopsy to obtain a tumor sample, unless not clinically feasible, at the time of radiographic disease progression. However, it is preferable that mandatory tumor biopsies be collected at the first evidence of radiographic response or at the first evidence of radiographic disease progression during treatment (within 40 days of radiographic progression or at the start of the next anti-cancer treatment, whichever is sooner).

Patients with disease progression or prior to the start of the next anti-cancer treatment, whichever is sooner: Acceptable samples include core-needle biopsies for deep tumor tissue (minimum three cores, if clinically feasible) or excisional, incisional, punch, or forceps biopsies for cutaneous, subcutaneous, or mucosal lesions.

- Optional tumor biopsies

Patients may agree to provide optional tumor biopsies by providing consent on the Optional Informed Consent Form, which is separate from the main study Informed Consent Form. For patients who agree to optional biopsies, biopsy samples may be collected per investigator's discretion at the time of radiographic response, and at the time of radiographic progression. Patients will need to have tumor lesions that the investigator deems to be safely accessible to a biopsy procedure, without unacceptable risk of a significant procedural complication.

For patients with a confirmed, prolonged CR and/or PR (e.g., of approximately 1 year in duration) who have an accessible residual mass, a biopsy of that residual mass is recommended to assess for viable TCs (vs. fibrotic or necrotic tissue).

Optional biopsies should consist of core-needle biopsies for deep tumor tissue or organs, or excisional, incisional, punch, or forceps biopsies for cutaneous, subcutaneous, or mucosal lesions.

Optional biopsy samples of enrolled patients will be evaluated for biomarkers using characterized assays for analysis of proteins, RNA, and DNA.

- Sample specifications

Tumor tissue samples consisting of core-needle biopsies of deep tumor tissue or lymph nodes or excisional, incisional, punch, or forceps biopsies of cutaneous, subcutaneous, or mucosal lesions will be obtained. Non-EBUS fine-needle aspirates, cell pellets from effusions or ascites, lavage samples, and bone biopsies are not permitted. [REDACTED]

RECIST target lesions are not to be biopsied.

Screening blood and prescreening tumor tissue samples, including those collected from patients who do not enroll in the study, may be used for future research and/or development of disease-related tests or tools.

For sampling procedures, storage conditions, and shipment instructions, see the laboratory manual.

Unless the patient gives specific consent for his or her leftover samples to be stored for optional exploratory research (see Section 4.5.14), biological samples will be destroyed no later than the time of completion of the final Clinical Study Report, with the following exceptions:

- Serum samples collected for PK or immunogenicity analysis may be needed for additional immunogenicity characterization and for PK and immunogenicity assay development and validation; therefore, these samples will be destroyed no later than 5 years after the final Clinical Study Report has been completed, or earlier depending on local regulations.
- Blood, plasma, serum, and tumor tissue samples collected for biomarker research will be destroyed no later than 15 years after the final Clinical Study Report has been completed or earlier, depending on local regulations, with the exception of tissue samples that undergo WGS or WES, which will be stored until they are no longer needed or until they are exhausted. However, the storage period will be in accordance with the IRB/EC-approved Informed Consent Form and applicable laws (e.g., health authority requirements).
- For enrolled patients, remaining archival tissue blocks will be returned to the site upon request or no later than 18 months after final closure of the study database, whichever occurs first. For patients who are not enrolled, remaining archival tissue blocks will be returned to the site after eligibility determination, if requested.
- Blood collected for WGS will be stored indefinitely, until depleted, or until a patient requests that his or her samples be destroyed.

When a patient withdraws from the study, samples collected prior to the date of withdrawal may still be analyzed, unless the patient specifically requests that the samples be destroyed or local laws require destruction of the samples. However, if

samples have been tested prior to withdrawal, results from those tests will remain as part of the overall research data.

Data arising from sample analysis will be subject to the confidentiality standards described in Section [8.4](#).

Given the complexity and exploratory nature of exploratory biomarker analyses, data derived from these analyses will generally not be provided to study investigators or patients unless required by law. The aggregate results of any conducted research will be available in accordance with the effective Sponsor policy on study data publication.

4.5.9 Electrocardiograms

An ECG is required at screening, at the treatment discontinuation/completion visit, and when clinically indicated. ECGs for each patient should be obtained from the same machine wherever possible. Lead placement should be as consistent as possible. ECG recordings must be performed after the patient has been resting in a supine position for at least 10 minutes.

For safety monitoring purposes, the investigator must review, sign, and date all ECG tracings. Paper copies of ECG tracings will be kept as part of the patient's permanent study file at the site. Any morphologic waveform changes or other ECG abnormalities must be documented on the eCRF.

4.5.10 Clinical Outcome Assessments

Patient-reported outcome data will be collected to document the treatment benefit and more fully characterize the clinical profile of tiragolumab plus atezolizumab.

Patient-reported outcome data will be collected using the following instruments: EORTC QLQ-C30, EORTC QLQ-LC13, a single item from EORTC IL46, and the EQ-5D-5L.

4.5.10.1 Data Collection Methods for Clinical Outcome Assessments

Paper versions of the PRO instruments will be self-administered by patients while on study treatment and then may be interviewer administered by site personnel to the patient over the telephone during the post-treatment follow-up in order that data may be collected without mandating that patients travel to the clinical site (see schedule of activities in [Appendix 1](#)). Patient-reported outcome data will be entered into the study database by the site personnel. The questionnaires will be translated into the local language as required. For patients who are unable to come into clinic due to government restrictions or personal safety, PROs may be completed by means of a telephone call; source documentation should be obtained, which includes, among other information, that the questionnaires were administered via telephone.

To ensure instrument validity and that data standards meet health authority requirements, questionnaires scheduled for administration during a clinic visit will be completed in their entirety by the patient prior to receiving any information on disease

status, prior to the performance of non-PRO assessments that could bias patients' answers, and prior to the administration of study treatment, unless otherwise specified.

PROs should be administered as outlined below:

- Patients' health status should not be discussed prior to administration of the instruments.
- Sites must administer the official version of each instrument, as provided by the Sponsor. Instruments must not be copied from the protocol.
- Sites should allow sufficient time for patients to complete the instruments.
- Sites should administer the instruments in a quiet area with minimal distractions and disruptions.
- Patients should be instructed to answer questions to the best of their ability; there are no right or wrong answers.
- Site staff should not interpret or explain questions, but may read questions verbatim upon request.
- Patients should not obtain advice or help from others (e.g., family members or friends) when completing the instruments.
- Site staff should review all completed instruments and should ask the patient to rectify any response that is not clearly marked in the appropriate location. If a response is missing, site staff should ask the patient to complete the item or confirm that the item was intentionally left blank.

Patient-reported outcomes (EORTC QLQ-C30, EORTC QLQ-LC13, EORTC IL46, and EQ-5D-5L) will be collected on Day 1 of Cycle 1 (baseline) prior to administration of study drug, and at every other study treatment cycle prior to the administration of study drug (i.e., on Day 1 of Cycles 3, 5, 7, etc.) until radiographic disease progression per RECIST v1.1, and at the study treatment discontinuation/completion visit. Patients who discontinue study treatment for any reason other than radiographic disease progression per RECIST v1.1 (e.g., toxicity, symptomatic deterioration) will complete PROs at each tumor assessment visit until radiographic disease progression per RECIST v1.1, withdrawal of consent, death, or study termination by the Sponsor, whichever occurs first.

During the post-treatment follow-up, PROs will be completed 3 months (\pm 30 days) and 6 months (\pm 30 days) following radiographic disease progression per RECIST v1.1 (or loss of clinical benefit for patients who continue study treatment after disease progression per RECIST v1.1). The PROs at 3 and 6 months after disease progression or after treatment discontinuation/completion visit may be collected by telephone.

Patients whose native language is not available with the questionnaires are exempted from completing all PRO assessments.

The Sponsor will not derive adverse events reports from PRO data (see Section 5.3.5.13).

4.5.10.2 Description of Clinical Outcome Assessment Instruments EORTC QLQ-C30, EORTC QLQ-LC13 and EORTC IL46

The EORTC QLQ-C30 is a validated, reliable self-reported measure (Aaronson et al. 1993; Fitzsimmons et al. 1999) (see [Appendix 5](#)). It consists of 30 questions that assess five aspects of patient functioning (physical, emotional, role, cognitive, and social), three symptom scales (fatigue, nausea and vomiting, and pain), GHS and QoL, and six single items (dyspnea, insomnia, appetite loss, constipation, diarrhea, and financial difficulties) with a recall period of the previous week. Scale scores can be obtained for the multi-item scales. The functioning and symptoms items are scored on a 4-point scale that ranges from "not at all" to "very much," and the GHS and QoL items are scored on a 7-point scale that ranges from "very poor" to "excellent." The EORTC QLQ-C30 module takes approximately 15 minutes to complete.

The EORTC QLQ-LC13 (see [Appendix 6](#)) is comprised of 13 lung cancer specific items and includes 11 disease-specific scales/items (dyspnea, coughing, hemoptysis, sore mouth, dysphagia, peripheral neuropathy, alopecia, pain in chest, pain in arm or shoulder, pain in other parts, pain medication) (Bergman et al. 1994). The QLQ-LC13 takes approximately 7 minutes to complete.

In addition, EORTC IL46 will be collected. This validated single-item question that assesses overall side effect impact (see [Appendix 5](#)).

EQ-5D-5L

The EQ-5D-5L is a validated self-reported health status questionnaire that is used to calculate a health status utility score for use in health economic analyses (EuroQol Group 1990; Brooks 1996; Herdman et al. 2011; Janssen et al. 2013) (see [Appendix 7](#)). There are two components to the EQ-5D-5L: a five-item health state profile that assesses mobility, self-care, usual activities, pain/discomfort, and anxiety/depression, as well as visual analog scale that measures health state. The EQ-5D-5L is designed to capture the patient's current health status. Published weighting systems allow for creation of a single composite score of the patient's health status. The EQ-5D-5L takes approximately 3 minutes to complete. It will be used in this study for informing pharmacoeconomic evaluations.

4.5.11 Blood Samples for Whole Genome Sequencing or Whole Exome Sequencing (for Patients at Participating Sites Only)

At participating sites, blood samples will be collected for DNA extraction [REDACTED] or WES to identify variants that are predictive of response to study drug, are associated with progression to a more severe disease state, are associated with acquired resistance to study drug, are associated with susceptibility to developing adverse events, can lead to improved adverse event monitoring or investigation, or can increase the

knowledge and understanding of disease biology and drug safety. DNA extracted from blood may be compared with DNA extracted from tissue to identify somatic variants by distinguishing germline variants from somatic variants. The samples may be sent to one or more laboratories for analysis.

[REDACTED]

[REDACTED]

For sampling procedures, storage conditions, and shipment instructions, see the laboratory manual.

[REDACTED]

Refer to Section [4.5.14.6](#) for details on use of samples after patient withdrawal, confidentiality standards for data, and availability of data from biomarker analyses.

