Several key aspects of the study design and study population are summarized below.

| | | | |
|------------------------|------------------|---|---|
| Phase: | Phase III | Population Type: | Adult patients |
| Control Method: | Standard of care | Population Diagnosis or Condition: | Patients with locally advanced, unresectable Stage III non-small cell lung cancer |

| | | | |
|------------------------------|---|---|-----------------------------|
| Interventional Model: | Parallel group | Population Age: | ≥ 18 years |
| Test Compound(s): | Tiragolumab (RO7092284) Atezolizumab (RO5541267) | Site Distribution: | Multi-site and multi-region |
| Active Comparator: | Durvalumab | Study Intervention Assignment Method: | Randomization |
| Number of Arms: | Two | Number of Participants to Be Enrolled: | Approximately 800 |

STUDY TREATMENT

The investigational medicinal products for this study are tiragolumab, atezolizumab, and durvalumab.

Test Products (Investigational Drugs)

Patients in the experimental arm will receive 1680 mg atezolizumab by IV infusion followed by 840 mg tiragolumab by IV infusion every 4 weeks (Q4W) on Day 1 of each 28-day cycle.

Comparator Arm

Patients in the comparator arm will receive durvalumab 10 mg/kg administered by IV infusion on Days 1 and 15 of each 28-day cycle or at a fixed dose of 1500 mg Q4W (for patients whose weight ≥ 30 kg), administered by IV infusion on Day 1 of each 28-day cycle. The decision to administer durvalumab every 2 weeks (Q2W) or Q4W is based on investigator's discretion in consultation with the patient and/or local standard of care. Patients enrolled in the comparator arm may switch from receiving durvalumab 10 mg/kg IV Q2W to 1500 mg IV Q4W (for patients whose weight ≥ 30 kg) dosing upon completion of their current 28-day cycle.

There will be no dose modifications, including dose reductions, for atezolizumab or tiragolumab in this study.

DURATION OF PARTICIPATION

Treatment may be continued for 13 cycles, in the absence of metastatic disease, as long as patients are experiencing clinical benefit, as assessed by the investigator, in the absence of unacceptable toxicity or symptomatic deterioration attributed to disease progression after an integrated assessment of radiographic data, biopsy results (if available), and clinical status. The total duration of study participation for each individual is expected to range from 1 day to approximately 8 years.

COMMITTEES

| | |

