4.2 METHOD OF TREATMENT ASSIGNMENT

4.2.1 Treatment Assignment

This is a Phase III, open-label, randomized study. After written informed consent has been obtained and eligibility has been established [REDACTED], the study site will obtain the patient's identification number and study treatment assignment from the interactive voice or web-based response system (IxRS).

Patients will be randomized to receive either tiragolumab plus atezolizumab or durvalumab. Randomization will occur in a 1:1 ratio through the use of a permuted-block randomization method to ensure a balanced assignment to each treatment arm. Randomization will be stratified according to the following criteria:

- ECOG Performance Status (0 vs. 1)
- PD-L1 expression, [REDACTED]
- Tumor histology of NSCLC (non-squamous vs. squamous)
- Staging (IIIA vs. IIIB or IIIC)

Staging will be performed according to the 8th revised edition of the AJCC/UICC NSCLC staging system (Stage IIIA vs. Stage IIIB or IIIC).

Patients should receive their first dose of study drug at randomization if possible. [REDACTED]

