Appendix 1: Schedule of Activities (cont.)

| Assessment/Procedure | Screening ^a | Treatment (28-Day Cycles) ^b | | Tx Discon or Completion Visit ^c | Post-Treatment Follow-Up |
|--|------------------------|--|-------------------|--|--------------------------|
| | Days –28 to –1 | Day 1 (± 3 days) | Day 15 (± 3 days) | ≤ 30 Days After Final Dose | |
| Atezolizumab by IV infusion ^w | | x | | | |
| Tiragolumab by IV infusion ^w | | x | | | |
| Concomitant medications ^x | x | x ⁱ | x ⁱ | x ⁱ | |
| Tumor assessment ^{y,z,aa} | x ^y | x ^{y,aa} | | | x ^y |
| PROs (EORTC QLQ-C30, EORTC QLQ-LC13, EORTC IL46, and EQ-5D-5L) ^{bb} | | x | | x | x |
| Adverse events ^{cc} | | x ⁱ | x ⁱ | x ⁱ | x |
| Serum sample for ADA assessment (central laboratory) ^{dd} | | Refer to Appendix 2 for the ADA sampling schedule. | | | |
| Serum sample for PK assessment (central laboratory) ^{dd} | | Refer to Appendix 2 for the PK sampling schedule. | | | |
| Blood sample for biomarkers (central laboratory) ^{ee} | | Refer to Appendix 2 for the biomarker sampling schedule. | | | |
| 

 | | At the time of response and/or radiographic progression | | | |
| Mandatory tumor biopsy ^{hh} | | At the time of response and/or radiographic progression (if clinically feasible) | | | |
| Well-being checks (for survival follow-up) ⁱⁱ | | | | | x |
| Anti-cancer therapy ⁱⁱ | | | | | x |

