### 4.1 **GENERAL CONSIDERATIONS**

The efficacy analyses will be performed in the PPAS and FAS, with patients grouped according to the treatment assigned at randomization by IxRS.

[figure not shown]
Safety analyses will be performed in the Safety Analysis Set (SAS), with patients grouped according to the actual treatment received. Specifically, a patient will be included in the tiragolumab plus atezolizumab arm if the patient received any amount of tiragolumab or atezolizumab, including the case when tiragolumab or atezolizumab was received in error, regardless of the initial treatment assignment at randomization.

Hypothesis tests will be two-sided unless otherwise indicated. Baseline measurements are defined as the last available measurement obtained prior to the patient receiving the first dose of any component of study treatment, or prior to randomization for patients who were not treated, unless otherwise noted.

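### The only PRO baseline is taken on Cycle 1 Day 1 of an open-label trial, and no visible text requires it to be completed before the patient learns the assigned arm

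*Protocol*

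**What the plan says.** **Timing of the baseline.** Protocol 4.5.10.1 states that the PROs "will be collected on Day 1 of Cycle 1 (baseline) prior to administration of study drug". In Appendix 1 the screening cell of the PRO row is empty, and the first entry is in the treatment Day 1 column.

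**Knowledge of the arm.** Protocol 4.2.1 reads "This is a Phase III, open-label, randomized study". Once consent and eligibility are in place, "the study site will obtain the patient's identification number and study treatment assignment" from the IxRS. The same section adds: "Patients should receive their first dose of study drug at randomization if possible". For the comparator arm, the synopsis says "The decision to administer durvalumab every 2 weeks (Q2W) or Q4W is based on investigator's discretion in consultation with the patient". It also names local practice as a basis for that choice.

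**Order-of-completion rules.** Protocol 4.5.10.1 requires clinic questionnaires to be finished before the patient hears about disease status, "prior to the performance of non-PRO assessments that could bias patients' answers", and before dosing. Disclosure of the arm is not on that list.

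**Baseline rule.** SAP 4.1: "Baseline measurements are defined as the last available measurement obtained prior to the patient receiving the first dose of any component of study treatment". A value before randomization is used only for patients who were never treated. Protocol 6.4 also ties baseline to the first dose.

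**Endpoint.** Protocol 6.5.2.8 and SAP 4.3.1.5 define TTCD for cough, dyspnea, chest pain, global health status (GHS) and physical functioning. The event is a change of at least 10 points from baseline, confirmed at a consecutive assessment or followed by death. Time runs from randomization. TTCD stands among the key secondary objectives in Table 1, summarized by a hazard ratio.

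**The concern.** A change score is only as sound as its reference value. In an open-label comparison of a new combination with standard care, patients may answer differently once they know their arm. If that moves the average baseline in one arm, the distance to a 10-point worsening differs between arms with no treatment effect behind it.

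The order-of-completion rules show that the sponsor thought about influences on answers, but they leave out the one created by open-label assignment. All five TTCD endpoints rest on this single value, as do the change-from-baseline summaries of the other scales. Adjusting for baseline would not repair the problem, because the covariate itself would carry the shift.

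**Working it through.** The documents give no power, effect size or event count for TTCD, so there is no planned figure to reproduce. The check has three parts.

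**1. Sequence permitted by the text.**
- Consent and eligibility, then the IxRS assignment (Protocol 4.2.1).
- First dose on the day of randomization if possible, so a gap is allowed (Protocol 4.2.1).
- Baseline PRO at any time on Cycle 1 Day 1 before the dose (Protocol 4.5.10.1).
- If dosing falls on a later day, the baseline form is completed after assignment. If it is the same day, either order complies.
- For durvalumab patients, consultation on the two-weekly or four-weekly schedule would disclose the arm. Its timing relative to the forms is not stated.
- Under SAP 4.1 the latest value before the first dose is used. If a form had been completed before randomization and another after it but before dosing, the later one would be the baseline.

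**2. Sensitivity of each scale to a small change at baseline.** With k items of L levels scored 0 to 100, the smallest step is 100/(k × (L − 1)). Item counts and levels come from Appendices 5 and 6.

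| Scale | k | L | Smallest step | Steps needed for ≥ 10 points |
|---|---|---|---|---|
| Cough | 1 | 4 | 100/3 = 33.3 | 1 (33.3) |
| Chest pain | 1 | 4 | 100/3 = 33.3 | 1 (33.3) |
| Dyspnea (LC13) | 3 | 4 | 100/9 = 11.1 | 1 (11.1) |
| GHS | 2 | 7 | 100/12 = 8.3 | 2 (16.7) |
| Physical functioning | 5 | 4 | 100/15 = 6.7 | 2 (13.3) |

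On the three symptom scales, one response category at baseline can create or remove the 10-point change. On cough or chest pain, a mean shift of 2 points means 2/33.3 = 6% of patients moving one category.

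**3. Illustrative simulation with no treatment effect.** All inputs are assumptions: a 15-step functioning scale, mean 75, between-patient SD 16, visit-to-visit SD 9, slow decline, 12 visits, and a 10-point drop confirmed at the next visit. The hazard ratio is the shifted arm against the other.

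Shift in one arm's baseline only, in the direction of worse reported function:

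| Mean shift (points) | 0 | 1 | 2 | 3 | 5 |
|---|---|---|---|---|---|
| TTCD HR | 0.99 | 0.89 | 0.80 | 0.69 | 0.53 |

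A 2-point shift in the better direction gives about the reciprocal, 1/0.80 = 1.25. Another set of assumed inputs (400 per arm, unadjusted Cox model) gives 1.14 for GHS and 1.18 for physical functioning. The spread of 1.14 to 1.25 reflects the choice of inputs.

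These figures assume that the reaction is gone by the first follow-up form at Cycle 3. If a 2-point better rating instead persists at every visit, the result depends on the baseline used:

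| Pattern of a 2-point better rating in one arm | TTCD HR |
|---|---|
| Baseline form only, current plan | 1.24–1.25 |
| Persists, current plan (Cycle 1 Day 1 baseline) | 0.98 |
| Persists, pre-randomization baseline | 0.77 |

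The documents do not indicate which pattern to expect.

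**The case against.** The strongest objection is the last table. Patients know their arm at every later form as well. If the reaction persists, it sits in both baseline and follow-up and nearly cancels under the current plan. A pre-randomization baseline would then expose an open-label reporting difference in the follow-up scores. This stands: the proposed change protects the reference value, not the later answers, and the simulated ratios cannot be read as an estimate of bias.

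Four further points also stand in part:
- **Timing.** A reader might infer that the baseline is always post-randomization. The documents do not show that: on a same-day schedule a site may hand out the forms before the IxRS request. The order is left open.
- **Redaction.** The footnote to the PRO row in Appendix 1 (bb) and the text after the sentence on dosing at randomization are not visible. Either could contain a safeguard.
- **Recall.** The GHS and LC13 items ask about the past week, which with same-day randomization lies almost wholly before assignment. This dampens the risk but does not remove it. On the printed QLQ-C30, the five physical functioning items come before the past-week heading, and EQ-5D-5L asks about today.
- **Repair.** A reader might infer that nothing can be done afterwards. Post-baseline scores can still be compared between randomized arms without subtracting baseline, and Protocol 6.5.2.8 already plans score summaries.

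**Conclusion.** The point holds as a risk of bias. The visible text permits the reference value for five key secondary endpoints, and for the other PRO change scores, to be collected after the patient knows the arm. Both baseline rules are tied to the first dose rather than to randomization.

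Size and direction are unknown. If durvalumab patients rated themselves worse at baseline, their later deterioration would be harder to reach, which would work against the experimental arm; the opposite reaction would favor it. A reader might infer that TTCD will be biased in favor of the combination, or by a stated amount. The documents support neither. They give no shift size, and the range of 1.14 to 1.25 for a 2-point shift depends on assumed score distributions and on a reaction that has faded by Cycle 3.

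IRF-assessed PFS is not affected.

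**What to change.** **Patients not yet randomized.** Require the baseline questionnaires after eligibility is confirmed and before the IxRS assignment is requested; the same day is acceptable. Amend Protocol 4.5.10.1 and the PRO row of Appendix 1. In the SAP, define the PRO baseline as the last assessment before randomization. SAP 4.1 already allows exceptions to its general baseline rule, so this fits there.

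**Patients already randomized.** Report baseline PRO scores by arm, since randomization should make them similar on average. Pre-specify a TTCD sensitivity analysis limited to patients whose baseline form is documented as completed before randomization, where recorded timing allows. The documents do not give enrolment status, so this may be the only part that can still be applied.

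**Cost.** A short amendment or site letter and a few lines in the SAP, with no additional questionnaire. The baseline may be a few days older when dosing is not on the day of randomization; Protocol 4.5 already accepts screening assessments up to 96 hours before Cycle 1 Day 1. Open-label reporting bias that persists in follow-up is not removed and should be acknowledged when TTCD is interpreted.
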